### **3.7.2.2 *Flu-Like Reactions***

Flu-like reactions (FLRs) will also be summarized by analysis period, treatment group and overall using the MedDRA coding system, by system organ class and preferred term. Number and percent of patients reporting at least one FLR will be summarized also.

Flu-like reactions are defined as AEs with following preferred term or verbatim: flu-like illness, chills, myalgia, arthralgia, pyrexia, feeling hot, or body temperature increased, starting on the day of injection or the next day.

Percentage of injections leading to flu-like reactions will be summarized by analysis period, treatment group, and overall using descriptive statistics.

Percentage of the injections leading to flu-like reactions will be calculated as follows for each patient:  $(A/B) * 100$ , where A = number of injections leading to flu-like reactions, and B = total number of injections.

### **3.7.2.3 *Adverse Events of Special Interest:***

Treatment-emergent Bleeding, Hypersensitivity/Immunogenicity, Hepatotoxicity, Nephro-toxicity adverse events will be summarized using MedDRA preferred term and system organ class. Relationship between Treatment-emergent Bleeding event and presence of Concomitant Anti-Coagulant or Anti-Platelet Medication will be explored. Concomitant anti-coagulant or anti-platelet medications include medications that were taken before or on bleeding event onset date/time and stopped on or after bleeding onset date/time or ongoing at the end of study.

The Bleeding TEAE will be defined based on the Haemorrhages (SMQ) Export from MedDRA.

The Hypersensitivity/Immunogenicity TEAE is defined as AEs with either of two condition 1) meet Hypersensitivity (SMQ) Export from MedDRA, or 2) preferred term “Drug specific antibody” or “Drug specific antibody present” within system organ class “Investigations”.

The Hepatotoxicity TEAE will be defined based on the Drug-related hepatic disorders – comprehensive search (SMQ) Export from MedDRA, excluding neoplasms.

The Nephrotoxicity TEAE will be defined based on, either the Acute Renal Failure (SMQ) Export from MedDRA, or Proteinuria (SMQ) Export from MedDRA.

Treatment-emergent bleeding adverse events will be listed as well.

### ***3.7.3 Vital Signs Measurements***

Vital signs will include weight, BMI, body temperature, heart rate, respiratory rate, and systolic, diastolic blood pressure, and [REDACTED]. Summary tables will be created by treatment group and overall to present the descriptive statistics (n, mean, standard error, standard deviation, median, P25, P75, minimum, and maximum) for vital sign values as well as the change from Baseline at each nominal study visit.

### ***3.7.4 Laboratory Measurements***

The following is the list of lab analytes that will be collected throughout the study:

- Chemistry: sodium, potassium, chloride, bicarbonate, total protein, albumin, calcium, magnesium, phosphorus, BUN (blood urea nitrogen), creatinine, creatinine clearance, estimated glomerular filtration rate, uric acid, total bilirubin, direct bilirubin, indirect bilirubin, alanine aminotransferase (ALT), aspartate aminotransferase (AST), alkaline phosphatase,
- Hematology: red blood cells, hemoglobin, hematocrit, MCV, MCH, MCHC, Platelets, white blood cells (WBCs), and WBC differential in both percentage and absolute count (Neutrophils, eosinophils, basophils, lymphocytes, and monocytes)
- Coagulation: aPTT, PT, international normalized ratio (INR)
- Complement: C5a, Bb
- Other assessments: Troponin I, hsCRP, Sedimentation Rate, [REDACTED]  
[REDACTED]
- Screening Tests: Hepatitis B surface antigen, Hepatitis C antibody, HIV antibody, FSH (women), serum  $\beta$ hCG (women), and HbA1c, TSH, T3, T4. The screening test data will only be displayed in patient listings.
- Urinalysis: color, appearance, specific gravity, pH, protein, blood, ketones, urobilinogen, glucose, bilirubin, leukocytes esterase, nitrate, and microscopic examination. For expanded urinalysis at certain visits, additional measurements will be performed including: total protein (quantitative), microalbumin, and  $\beta$ 2-microglobulin. The expanded urinalysis data will be only displayed in patient listings.

Missing WBC differential absolute counts and percentages will be derived:

If WBC differential absolute counts are missing, and percentages are available, then absolute counts will be calculated by multiplying the percentage by total WBC count. Conversely, if absolute count is available, and percentage is missing, then percentage will be calculated by dividing absolute count by the total WBC count. If neutrophil counts and percentages are missing, and segmented neutrophil and band neutrophil results are available, then neutrophils will be calculated by adding segmented neutrophils and band neutrophils.

Quantitative laboratory measurements reported as ‘< X’, i.e. below the lower limit of quantification (BLQ), or ‘> X’, i.e. above the upper limit of quantification (ULQ), or ‘Cannot calc’, i.e. outside the limit of quantification, will be converted to X (or limit of quantification) for the purpose of quantitative summaries.

The MDRD equation will be used to calculate estimated Glomerular Filtration Rate (GFR) base on central lab serum creatinine ( $\mu\text{mol/l}$ ) as:

$\text{eGFR (mL/min/1.73m}^2\text{)} = 32788 \times \text{Serum Creatinine } (\mu\text{mol/l})^{-1.154} \times \text{Age } ^{-0.203} \times (1.210 \text{ if Black or African American}) \times (0.742 \text{ if female}).$

Chemistry, hematology, coagulation, complement, other assessments and quantitative urinalysis (result, change from Baseline) will be summarized using descriptive statistics (n, mean, standard error, standard deviation, median, P25, P75, minimum, and maximum) and urinalysis dipstick protein will be summarized by frequency counts by treatment group, overall, and by nominal study visit.

The number and percent of patients falling in each of the following category after first dose will be tabulated by treatment group and overall, for each analysis period:

- The higher of  $\text{ALT} > 3 \times \text{ULN}$  or  $\text{ALT} > 2 \times \text{Baseline}$
- $\text{ALT/AST} > 3 \times \text{ULN}$
- $\text{ALT/AST} > 5 \times \text{ULN}$
- $\text{ALT/AST} > 8 \times \text{ULN}$
- $\text{ALT/AST} > 10 \times \text{ULN}$
- $\text{ALT/AST} > 20 \times \text{ULN}$
- $\text{ALT} > 3 \times \text{ULN} - \leq 5 \times \text{ULN}$
- $\text{ALT} > 5 \times \text{ULN} - \leq 10 \times \text{ULN}$
- $\text{ALT} > 10 \times \text{ULN} - \leq 20 \times \text{ULN}$
- Total bilirubin  $> 2 \times \text{ULN}$
- $\text{ALP} > 2 \times \text{ULN}$  and (baseline  $\text{ALP} < 2 \times \text{ULN}$  or baseline  $\text{ALP}$  missing)

The number and percent of patients falling in each of the following categories based on confirmed results after first dose will be tabulated by treatment group, and overall for each analysis period (a confirmed value is based on a consecutive lab value performed on a different day to, but within 7 days of, the initial value. If that value is in the same or worse category then the initial value is confirmed. If the consecutive value is in a better category then the initial value is confirmed using the consecutive value category. If there is no retest within 7 days then the initial value is presumed confirmed. If there are multiple results on the same day, then the worst value will be utilized in the analysis):

- The higher of  $\text{ALT/AST} > 3 \times \text{ULN}$  or  $\text{ALT/AST} > 2 \times \text{Baseline}$ , which is confirmed
- $\text{ALT/AST} > 3 \times \text{ULN}$ , which is confirmed
- $\text{ALT/AST} > 5 \times \text{ULN}$ , which is confirmed
- $\text{ALT/AST} > 10 \times \text{ULN}$ , which is confirmed
- $\text{ALT/AST} > 20 \times \text{ULN}$ , which is confirmed

For patients having confirmed 3-fold or greater elevations above the ULN for ALT or AST, a listing of all of the ALT, AST, total bilirubin, INR, and alkaline phosphatase records will be provided. Other liver abnormalities including elevation of ALT ( $> 3 \times$  ULN) accompanied by elevated total bilirubin ( $> 2 \times$  ULN), elevation of ALT ( $> 3 \times$  ULN) accompanied by INR  $> 1.5 \times$  ULN, elevation of ALT ( $> 3 \times$  ULN) accompanied by elevated total bilirubin  $> 2 \times$  ULN and ALP  $< 2 \times$  ULN, and elevation of ALT/AST in temporal association with nausea, vomiting, anorexia, abdominal pain, or fatigue will be reviewed by the study team and summarized if needed.

The following hematology and hepatic enzymes lab results will be graded based on Toxicity Grading Scale for Healthy Adult and Adolescent Volunteers Enrolled in Preventive Vaccine Clinical Trials (September 2007), and the incidence of shift from Baseline to worst post-baseline value will be summarized for each analysis period. Post-baseline lab results are defined as any assessment taken after the first dose. If a patient is missing a baseline value but has a post-baseline value, then the baseline assessment will be labeled as “unknown”. Likewise, if a patient has a baseline value but has no post-baseline values, then the worst value will be labeled as “unknown”. Number and proportion of patients with shift from baseline to worst post-baseline values based on the confirmed results by toxicity grade for GFR, ALT, AST, and platelets will also be tabulated.

- Hemoglobin: shift from Baseline to minimum post-baseline value
- WBCs: shift from Baseline to minimum post-baseline value
- Platelets: shift from Baseline to minimum post-baseline value
- Creatinine: shift from Baseline to maximum post-baseline value
- BUN: shift from Baseline to maximum post-baseline value
- eGFR: shift from Baseline to minimum post-baseline value
- Proteinuria: shift from Baseline to worst post-baseline value
- ALT: shift from Baseline to maximum post-baseline value
- AST: shift from Baseline to maximum post-baseline value
- Alkaline phosphatase: shift from Baseline to maximum post-baseline value

### ***3.7.5 Exposure***

Treatment duration and amount of Study Drug received will be summarized by Randomized Treatment Period and OLE period, and by treatment group and overall for the SAF1 and SAF2. Treatment duration is defined as the last day on Study Drug in a specific period minus the first day on Study Drug in the analysis period plus one day.

Compliance to Study Drug will be summarized by descriptive statistics by treatment, and in total, for each period.

Compliance will be calculated as follows:

$$100 \times (\text{number of injections of Study Drug}) / (\text{number of injections scheduled during the treatment period}).$$

Note that number of injections scheduled during the treatment period will be calculated as the Study Week of the last dose for patients did not get dose adjustment to biweekly. For patients who got dose adjustment to biweekly, if the dose adjustment started at Week x, then number of injections scheduled during the treatment period will be calculated as x plus the largest integer that is less than or equal to (study week of the last dose minus x) divided by 2, [number of weeks on weekly dose + integer of (number of weeks on bi-weekly dose)/2 ]

For early withdrawals/terminations, the number of injections will be calculated for the period up to their withdrawal/termination.

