## 8. TREATMENT OF PATIENTS

### 8.1 Study Drug Administration

For each individual patient, Study Drug will be administered SC as a single 1.5 mL injection once-weekly for Weeks 1-52 of the Randomized Treatment period of the study, and Weeks 53-104 of the OLE period of the study. Self-administration will be allowed after appropriate training of patient and/or caregiver.

Patients should receive 1 dose per week, with weeks always defined relative to Study Day 1. For example, if a patient receives the first dose on a Monday, subsequent doses should be given on Mondays, if possible. If a patient misses an injection, or if dosing on the usual day is not possible, the patient can reschedule the injection provided that 2 doses are administered at least 2 days apart.

Please refer to the Study Drug Manual provided by the Sponsor for more detailed instructions for Study Drug preparation and administration.

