### **8.6.3 Stopping Rules for Platelet Count Results**

Actions to be taken in the event of a low platelet count are summarized in [Table 4](#) below.

In the event of a platelet count less than  $75,000/\text{mm}^3$  that is associated with major bleeding or clinically-relevant non-major bleeding (defined below; [Schulman et al. 2005](#)), dosing of a patient with Study Drug will be stopped permanently. The follow-up schedule for any events meeting this stopping criterion will be determined by the Investigator in consultation with the Sponsor Medical Monitor.

In the event of any platelet count less than  $50,000/\text{mm}^3$ , or a platelet count less than  $75,000/\text{mm}^3$  that occurs while the patient is on dosing at 300 mg every 2 weeks then dosing of a patient with volanesorsen will be stopped permanently. Platelet count will be monitored as outlined in [Table 4](#).

Administration of corticosteroids is recommended for patients whose platelet count is less than  $50,000/\text{mm}^3$ . Recovery in platelet count may be accelerated by administration of high dose corticosteroids. Treatment guidelines for immune thrombocytopenia ([Provan et al. 2010](#)) recommend dexamethasone 40 mg daily for 4 days every 2-4 wk for 1-4 cycles; prednisolone 0.5-2 mg/kg/day for 2-4 weeks then taper; or methylprednisolone 30 mg/kg/day for 7 days (**note:** may require continuation with oral corticosteroids after methylprednisolone).

Triglyceride levels will be monitored weekly, and AE monitoring will continue during corticosteroid treatment and the laboratory alert will be changed from an increase of 2,000 to 500 mg/dL during that period.

In the event of a platelet count less than  $75,000/\text{mm}^3$ , and in the absence of major bleeding or clinically-relevant non-major bleeding (defined below; [Schulman et al. 2005](#)), dosing of a patient with Study Drug will be suspended temporarily until the platelet count has recovered to  $\geq 100,000/\text{mm}^3$ . If dosing is reinitiated it should be at a reduced dose frequency of 300 mg every 2 weeks (refer to [Section 8.7](#)). The suitability of the patient for reinitiation of dosing will be determined by the Investigator in consultation with the Study Medical Monitor and will be based on factors such as the original rate of decline in the patient's platelet count, whether any bleeding events were experienced by the patient, and the speed of recovery of platelet count upon holding of dosing.

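### Read literally, the SAP 3.7.5 compliance denominator halves compliance for a fully dosed OLE Year 1 patient, drops doses missed after the last one taken, and has no term for ordered pauses

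*SAP*

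**What the plan says.** SAP 3.7.5 defines compliance as 100 times the injections given divided by the "number of injections scheduled during the treatment period". It adds that "Compliance to Study Drug will be summarized by descriptive statistics by treatment, and in total, for each period". Exposure in that section is split into the Randomized Treatment Period and the OLE period.

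The denominator is then fixed by rule:

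- Weekly dosing throughout: "Note that number of injections scheduled during the treatment period will be calculated as the Study Week of the last dose".
- Change to every-2-week dosing at Week x: "x plus the largest integer that is less than or equal to (study week of the last dose minus x) divided by 2". A bracket restates this as the weeks on weekly dosing plus the integer part of half the weeks on biweekly dosing.
- A closing sentence: "For early withdrawals/terminations, the number of injections will be calculated for the period up to their withdrawal/termination".

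On week numbering, Protocol 8.1 counts weeks from Study Day 1, which the protocol glossary defines as the day of first dose, and places open-label dosing in "Weeks 53-104 of the OLE period of the study". Protocol 4.4 equates Study Week 65 with Week 13 of the OLE. The protocol's open-label schedule (Appendix A) carries OLE-relative weeks in a separate row with its own label. SAP 2.1.5 puts the end of the second OLE year at Week 156.

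On pauses, Protocol 8.6.3 says that, for a low platelet count without relevant bleeding, "dosing of a patient with Study Drug will be suspended temporarily until the platelet count has recovered to" a stated level. Protocol 8.6.4 and 8.5.9 also suspend dosing after a first documented severe hypoglycaemic event and during acute pancreatitis. Protocol 8.5.3 provides for planned interruptions for travel.

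**The concern.** Compliance is the only planned summary that compares doses given with doses due. Four features of the rule can make it misreport that comparison:

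1. A per-period numerator is set against a week number that does not restart in the OLE.
2. The denominator stops at the last dose taken, so doses missed after it cannot count.
3. Weeks in which the protocol suspended dosing count as doses due.
4. Week x, on which the every-2-week rule turns, is not defined.

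The end point of the count matters here because SAP 3.1 and 3.8 record that study treatment was discontinued before the protocol-specified treatment period was complete. The pause issue may not fall evenly on the arms: Protocol 2.3.4 reports a platelet decrease associated with the active drug in Phase 2. The documents do not allow that imbalance to be sized.

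**Working it through.** The documents state no compliance figure, so there is none to reproduce. The rule is applied as written. Let W be the Study Week of the last dose. The denominator is D = W for weekly dosing and D = x + floor((W − x)/2) after a change at Week x. Compliance is 100 × doses/D.

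**Baseline case.** Randomised period, weekly dosing, no pause, all doses taken: 52/52 = 100%. The rule works here.

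**1. Week origin in the OLE**

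- Year 1, all 52 open-label doses, last dose in Study Week 104: 52/104 = 50%.
- Both OLE years, all 104 doses, last dose in Study Week 156: 104/156 = 66.7%.
- Weekly in Study Weeks 53 to 59, then every 2 weeks from Week 60 to Week 104, nothing missed: 7 + 23 = 30 doses; D = 60 + floor(44/2) = 82; 30/82 = 36.6%.
- Year 1 with OLE-relative weeks: 52/52 = 100%.

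**2. End of the count (randomised period)**

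- Injects weekly to Week 39, then stops, stays in the period and is not recorded as terminated: 39/39 = 100%. Against the full period it is 39/52 = 75%.
- Injects weekly to Week 10 and is withdrawn at Week 20 (weeks assumed for illustration): 10/10 = 100% if the closing sentence governs only the numerator, or 10/20 = 50% if it governs the denominator. The SAP does not say which.

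**3. Protocol-directed pauses (randomised period, every permitted dose taken)**

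- Six-week pause, weekly dosing resumed, last dose in Week 52: 52 − 6 = 46 doses; 46/52 = 88.5%.
- Shorter and longer pauses on the same pattern: 2 weeks 50/52 = 96.2%; 4 weeks 48/52 = 92.3%; 8 weeks 44/52 = 84.6%.
- Platelet pattern, where Protocol 8.6.3 has any restart at every 2 weeks. Weekly in Weeks 1 to 10, paused in Weeks 11 to 16, every 2 weeks from Week 17 to Week 51: 10 + 18 = 28 doses. With x = 17, D = 17 + floor(34/2) = 34 and compliance is 82.4%. With x = 11, D = 11 + floor(40/2) = 31 and compliance is 90.3%.

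Pause lengths are assumed; the documents give no distribution.

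**4. Meaning of Week x (x = 20, W = 52)**

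- The rule gives 20 + floor(32/2) = 36.
- If Week 20 is the first every-2-week dose, the bracket gives 19 + floor(33/2) = 35, one fewer.
- If Week 20 is the last weekly week, the bracket gives 20 + floor(32/2) = 36 and the two agree.

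**The case against.** The best defence is that a period count was meant. SAP 3.7.5 speaks of injections scheduled during the treatment period, reports by period, and computes treatment duration within the period. Elsewhere the SAP re-bases the OLE to its own first dose (3.2.1), and Appendix B uses a period-week column. This makes the intention likely but leaves the rule unchanged: where the SAP means OLE-relative time in 3.2.3 it attaches the OLE label, and 3.7.5 does not. A programmer would have to depart from the text to obtain 100%. A reader might still infer that every OLE compliance figure will be wrong. That goes too far, because the figures depend on the literal reading with OLE doses alone in the numerator.

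A reader might also infer that anyone who stops injecting scores 100%. That does not hold generally. In the OLE, the literal rule gives a patient who stops after 10 doses 10/62 = 16.1%. In the randomised period the closing sentence may catch patients recorded as terminated. The exposed group is those who stop without such a record.

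On pauses, counting suspended weeks is defensible if compliance is meant to show how much of the weekly regimen was delivered. That objection stands in part. It is a reason to show paused weeks openly and not simply to remove them. Treatment duration and amount of drug are already summarised.

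A flat contradiction between the every-2-week rule and its bracket is another tempting reading. It is not established: it arises under one meaning of Week x and vanishes under the other, and it is worth one dose.

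**Conclusion.** The point holds as a defect in a stated rule. Literally applied, it gives 50% for complete OLE Year 1 dosing and 67% for both OLE years. In the randomised period it can show 100% where 75% is the fair figure, and it scores a 6-week ordered pause at 88.5% with no permitted dose missed. These results rest on Study Week being continuous from Study Day 1, as the protocol uses the term, on a numerator restricted to the period reported, and on the illustrative stopping and pause weeks above.

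The consequence is limited. Compliance is descriptive. The Per Protocol Set, the only analysis set with a dose-count criterion (Protocol 10.3), is dropped in SAP 3.8. A reader might infer that efficacy conclusions are at risk; the documents do not support that, since no endpoint, test or analysis set uses compliance. A separate figure for OLE Year 2 alone should not be inferred either, because SAP 3.7.5 specifies no such summary.

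**What to change.** Amend SAP 3.7.5 as follows:

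- Count weeks from the first dose of the period being summarised.
- Run the denominator to the earliest of period end, documented permanent discontinuation or withdrawal, in place of the last dose taken, and reword the closing sentence to match.
- Define Week x as either the last weekly week or the first every-2-week dose, and delete the bracketed text or align it with the rule.
- Report protocol-directed pause weeks as a separate row, and show compliance with those weeks excluded where the dosing records identify them.

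The cost is a few lines of SAP text, some programming, and a check that pause dates can be recovered from the collected data. That check is needed. Protocol 9.5.3 says only that dosing details go on the Dosing CRF. The action categories in Protocol 9.4.3.3 cover interruption with restart at the same dose and a reduced schedule, but have no single category for a pause followed by restart at lower frequency. No new data collection is proposed.

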### ***3.7.6 Physical Examination***

Abnormal changes in physical examinations that are deemed clinically-significant by the Investigator will be classified as adverse events. Physical examination results will be listed by labeled visit.

### ***3.7.7 12-Lead Electrocardiogram***

ECGs will be performed in triplicate at the visits indicated in the protocol Schedule of Procedures. The ECG data will include ventricular rate, PR interval, QRS duration, QT and corrected QT intervals, and overall interpretation. For the continuous variables, the average of measurements at a given visit will be used for analysis. For overall interpretation, the worst categorical results of triplicate results and the associated findings will be used for analysis. For the continuous variables above, descriptive statistics (n, mean, standard error, standard deviation, median, P25, P75, minimum, and maximum) of the results, as well as the change from Baseline to each study visit, will be presented by treatment group, and overall in summary tables; for the categorical responses to overall interpretation, counts and percentages will be provided.

All the data collected in triplicate will be listed.

